3.7.2 Post-hoc Endpoint Analysis

3.7.2.1 Slope of the change in eGFR

The slope of the change in the estimated GFR was derived from the individual slopes for each patient using the MDRD-4 equation. Descriptive statistics will be provided for each cohort [REDACTED]. The change from baseline in the estimated GFR will be calculated two ways. The first using the first and last timepoint for each subject and the second using all of the available timepoints.

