- j. Follow-up Treatment Period visits to be performed monthly (every 28 ± 3 days). These visits are only for those subjects who are continuing on study treatment beyond the initial 28-day Early Treatment Period. For those subjects continuing on study beyond 12 months, visits will occur every 2 months ± 3 days. Now that the MTD for daily dosing has been established, if it results in a dose increase for subjects not already receiving the MTD, the study assessments required for the monthly follow-up visits (ie, PK and postdose ECG and vital sign measurements not required) should be performed on Days 1 and 14 of the first month, then monthly for a total of 6 months, then every 2 months thereafter. The same schedule of evaluation will apply to any subjects increased from 50 mg/day to 100 mg/day after 6 months of treatment at 50 mg/day and after the 100 mg dose group is determined not to be a DLT dose cohort. Section 9.6 for study assessments to be performed and the timing of visits.
- k. End-of-Study visit is to be performed 30 days (± 3 days) after last dose of study drug.
- 1. Echocardiograms are to be obtained at Screening, on Day 28, and at Months 3, 6 every 6 months thereafter, and End-of-Study visit and are to include measurement of ejection fraction and assessment for pericardial effusion. Note: If subject has had echocardiogram within 2 months of End-of-Study visit, no need to obtain echocardiogram at End of Study visit. For those subjects who have already had their Month 12 visit, this may be performed at Month 13 and then subsequent echocardiograms may be performed on the same schedule as the MRIs. If pericardial effusion is diagnosed via echocardiogram, subject should be rechecked within 1–3 months to monitor for progression.
- m. Screening MRI should be performed following informed consent and prior to other Screening assessments. Results must be reviewed before the first dose of study drug is administered. MRI to be performed at Month 6 and then every 6 months thereafter. Note: If subject has had MRI within 3 months of End of Study visit, there is no need to obtain MRI at End-of-Study visit.
- n. Subjects on the Phase 1b portion of the study will have study drug held for a one-time drug holiday of at least 14 and up to 28 days with creatinine and cystatin C measurements performed before and immediately after the drug holiday, as well as a predose PK sample prior to restarting study drug.

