The initial data from this study (Protocol KD019-101) indicate that subjects with ADPKD receiving tesevatinib have experienced elevations of creatinine without elevations in cystatin C. The median changes from screening values for creatinine and cystatin C from all 9 subjects in the 50-mg dose cohort reveal that creatinine values were increased by 7.5% at Day 3, by 22% at Day 7, and increased by 13% at Day 28. Data after Day 28, including 2 subjects who have received tesevatinib for 16 months, do not indicate any significant ongoing change in creatinine. Cystatin C levels, during the same time periods, did not change (median decreases of 4.5%, 1%, and 4% at Days 3, 7, and 28, respectively). Data from the 8 subjects enrolled into the 100-mg dose cohort, as well as subjects enrolled in subsequent cohorts, exhibited a similar pattern. This increase in

creatinine occurs early and after approximately 7 days, does not continue to increase, similar to the increase in serum creatinine seen with cimetidine. Increases in creatinine were seen in previous clinical studies of tesevatinib. For example, increases in serum creatinine in 10% of subjects were reported in Study XL647-201. However, most of the previous studies were in subjects with malignancies, and in previous studies, cystatin C levels were not evaluated, so increases in serum creatinine that may not represent renal dysfunction were not recognized.

In order to further investigate the effects of tesevatinib on serum creatinine levels, the effects of tesevatinib on a panel of transporter molecules (including OCT2 and MATE) were evaluated in vitro. Preliminary results indicate that tesevatinib potently inhibits MATE1 and MATE2-K transporter proteins. MATE transporter proteins carry creatinine out of kidney proximal tubule cells into the tubule lumen. Inhibition of MATE transporter proteins decreases secretion of creatinine into the proximal tubule lumen and leads to an increase in serum creatinine levels. To demonstrate the reversible nature of the creatinine elevations, subjects on the Phase 1b portion of the study will have study drug held for a one-time drug holiday of at least 14 and up to 28 days with creatinine and cystatin C measurements before and immediately after the drug holiday, as well as a predose PK sample prior to restarting study drug.

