9.2.3 Drug Holiday

All subjects will undergo a 28-day drug holiday after 28 days of treatment with tesevatinib. During this drug holiday and for 4 weeks after the holiday, subjects will have the following procedures performed:

- Serum creatinine and serum cystatin C tests by central laboratory
- Tesevatinib plasma concentration
- Concomitant medications
- Adverse events

The blood samples for serum creatinine, serum cystatin C, and tesevatinib plasma concentration can be drawn in the clinic or at the subject's home, by the study's remote nursing vendor.

If the subject has the blood samples drawn at home, the study team should call the subject on that same day to collect the concomitant medication and adverse event information

The first day of the drug holiday will be the day after the Day 28 Study Visit. At the completion of the 28-day drug holiday, subjects will return for the month 2 study visit.

9.2.4 Month 2

Following the 28-day drug holiday subjects will return to the clinic for the month 2 visit (\pm 1 day) and the following procedures will be performed:

- Limited physical examination, including weight (See Section 9 for a listing of systems to be examined/reviewed)
- Vital sign measurements
- Supine 12-Lead ECG (to be performed predose prior to collection of any time-matched blood samples (repeat 3 times consecutively within 30 minutes [must have an interval of at least 1-2 minutes between ECGs])

Note: If QTc(F) is > 60 msec above highest average predose reading (average of baseline and screening) or to the level of \geq 480 msec, refer to Section 11.3.3. This should be done based upon the local site analysis.

- Clinical laboratory tests by central laboratory
- Study drug administration
- Concomitant medications
- Adverse event assessment
- Blood samples for PK analysis (to be collected predose at the Month 2, 3, 4, 5 and 6 visits only)
- Dispense/collect study drug

All subjects will have a collection of blood samples for serum creatinine, cystatin C, and tesevatinib concentration weekly for an additional 3 weeks after the Month 2 visit, to be collected pre-dose. These blood samples can be drawn in the clinic or at the subject's home, by the study's remote nursing vendor.

Adverse event and concomitant medication information will also be collected at these weekly visits. If the subject has the blood samples drawn at home, the study team should call the subject on the same day to collect this information

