Appendix A: Equations to Predict Glomerular Filtration Rate (MDRD-4, CKD-EPI_{2012cys}, and CKD-EPI_{2012Scr-cys})

4-Variable Modification of Diet in Renal Disease (MDRD-4) Equation

High Level Formula for Black or African-American Males:

Estimated GFR =
$$175 \times (Creatinine^{-1.154}) \times (Age^{-0.203}) \times 1.212$$

High Level Formula for Males NOT Black or African-American (any other option):

Estimated GFR =
$$175 \times (Creatinine^{-1.154}) \times (Age^{-0.203})$$

High Level Formula for Black or African-American Females:

Estimated GFR =
$$175 \times (Creatinine^{-1.154}) \times (Age^{-0.203}) \times 1.212 \times 0.742$$

High Level Formula for Females NOT Black or African-American (any other option):

Estimated GFR =
$$175 \times (Creatinine^{-1.154}) \times (Age^{-0.203}) \times 0.742$$

CKD-EPI_{2012cys} Equation to Predict Glomerular Filtration Rate (GFR)

Gender	Scys (mg/L)	Equation
female	≤ 0.8	$133 \times (\text{Scys/0.8})^{-0.499} \times 0.996^{\text{age}} (\times 0.932)$
	> 0.8	$133 \times (\text{Scys/0.8})^{-1.328} \times 0.996^{\text{age}} (\times 0.932)$
male	≤ 0.8	$133 \times (\text{Scys/0.8})^{-0.499} \times 0.996^{\text{age}}$
	> 0.8	$133 \times (\text{Scys/0.8})^{-1.328} \times 0.996^{\text{age}}$

Note: Age is shown as years.

Scr = serum creatinine; Scys = serum cystatin C; CKD-EPI_{2012cys} = cystatin C-based CKD-EPI equation developed in 2012

CKD-EPI _{2012Ser-evs}	Equation	to	Predict	Glomerular	Filtration	Rate	(GFR)
CILD LI IZUIZSCI-CVS	Lquution	·	1 I Cuict	Giomici aiai	I IIII WUIDII	12000	()

Gender	Scr (mg/dL)	Scys (mg/L)	Equation
female	≤ 0.7	≤ 0.8	$130 \times (\text{Scr/0.7})^{-0.248} \times (\text{Scys/0.8})^{-0.375} \times 0.995^{\text{age}} (\times 1.08, \text{ if black})$
		> 0.8	$130 \times (\text{Scr/0.7})^{-0.248} \times (\text{Scys/0.8})^{-0.711} \times 0.995^{\text{age}} (\times 1.08, \text{ if black})$
	> 0.7	≤ 0.8	$130 \times (\text{Scr/0.7})^{-0.601} \times (\text{Scys/0.8})^{-0.375} \times 0.995^{\text{age}} (\times 1.08, \text{ if black})$
		> 0.8	$130 \times (\text{Scr/0.7})^{-0.601} \times (\text{Scys/0.8})^{-0.711} \times 0.995^{\text{age}} (\times 1.08, \text{ if black})$
male	≤ 0.9	≤ 0.8	$135 \times (\text{Scr/0.9})^{-0.207} \times (\text{Scys/0.8})^{-0.375} \times 0.995^{\text{age}} (\times 1.08, \text{ if black})$
		> 0.8	$135 \times (Scr/0.9)^{-0.207} \times (Scys/0.8)^{-0.711} \times 0.995^{age} (\times 1.08, if black)$

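### The all-timepoints eGFR slope mixes on-drug and off-drug creatinine, and SILK's mandatory drug holiday adds a spurious decline on top of the one that the other Phase 2a 50 mg daily cohort also carries

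*SAP*

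**What the plan says.** SAP 3.7.2.1 is a post hoc, descriptive analysis. The slope is "derived from the individual slopes for each patient using the MDRD-4 equation", summarised by cohort, and obtained two ways: "The first using the first and last timepoint for each subject and the second using all of the available timepoints". Neither this section nor the rest of the SAP says how samples taken off drug are to be treated.

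For SILK, Protocol 9.2.3 states: "All subjects will undergo a 28-day drug holiday after 28 days of treatment with tesevatinib". The holiday procedures include "Serum creatinine and serum cystatin C tests by central laboratory", scheduled weekly (Table 4-1). Dosing resumes at the Month 2 visit, so the predose sample at that visit is also off drug.

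Outside SILK, Table 4-2 footnote n gives the holiday to Phase 1b: "Subjects on the Phase 1b portion of the study will have study drug held for a one-time drug holiday". The 15 Phase 2a subjects on 50 mg daily have none. Every cohort has an End-of-Study visit 30 days after the last dose.

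On mechanism, Protocol 5.2.2.2.3 reports higher creatinine without higher cystatin C and explains it as follows: "Inhibition of MATE transporter proteins decreases secretion of creatinine into the proximal tubule lumen and leads to an increase in serum creatinine levels". The synopsis (Safety Assessments) expects the effect to reverse off drug; the holiday is there to demonstrate this.

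**The concern.** MDRD-4 eGFR falls when creatinine rises for any reason. If the drug raises creatinine without changing GFR, eGFR steps down on drug and back up off drug. A straight line through both states reads the step as a trend.

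Both Phase 2a 50 mg daily cohorts start from an off-drug baseline followed by on-drug values, so both lines tilt down. SILK then adds about four more high, off-drug values within the first two months, followed only by lower on-drug values until treatment ends. That steepens SILK further.

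SILK is up to 50 of the 65 subjects at 50 mg daily and was chosen to match the population considered for Phase 3. A steeper SILK slope could be read as faster progression in large kidneys, or as lack of effect, when part of it comes from the dosing calendar. A holiday meant to show that the creatinine rise is not renal damage would reappear as apparent renal decline.

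**Working it through.** **The plan's own figure.** The documents give no figure for the slope analysis. The nearest is the 80% confidence half-width for the mean 6-month change (SAP 3.1.2): 1.2816 × 4.0/√65 = 0.636, which reproduces the stated ±0.64 mL/min. The same section expects -2.5 mL/min over 6 months, or about -5 per year if linear.

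**Inputs from the documents**
- MDRD-4 is proportional to creatinine^-1.154 (Protocol Appendix A; SAP 3.7).
- Median creatinine rise at 50 mg: 7.5% at Day 3, 22% at Day 7, 13% at Day 28, in 9 Phase 1b subjects (Protocol 5.2.2.2.3).
- Half-life about 70 hours (Protocol 5.4.2). The holiday lasts 28 × 24/70 = 9.6 half-lives.
- SILK entry eGFR 35 to 80.

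**Assumptions.** True GFR slope 0; rise 13%; full reversal off drug; baseline 57.5, the midpoint of 35 to 80; screening at Day -14.

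**Size of the step.** 57.5 × 1.13^-1.154 = 57.5 × 0.868 = 49.9, a fall of 7.6 with no GFR change.

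**Values during the holiday.** The remaining creatinine rise is 13% × 0.5^(hours since Day 28/70). This gives eGFR of about 55.9, 57.2, 57.4 and 57.5 at Days 35, 42, 49 and 56.

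**Slopes.** Least squares per subject, multiplied by 365.25.
- SILK visits: Days -14, 1, 7, 14, 21, 28; holiday 35, 42, 49, 56; then 63, 70, 77; every 28 days from Day 84 to Month 12; every 60 days after that.
- Phase 2a 50 mg daily visits: Days -14, 1, 3, 7, 14, 21, 28, 56; then the same from Day 84.
- The on-drug value is taken as constant at 49.9.

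| mL/min/1.73 m² per year | 6 months | 12 months | 24 months |
|---|---|---|---|
| SILK, all timepoints | -11.5 | -5.3 | -2.3 |
| SILK without the four holiday values | -9.5 | -3.2 | -1.2 |
| Phase 2a 50 mg daily, all timepoints | -8.0 | -3.0 | -1.2 |
| SILK, on-drug values only | 0 | 0 | 0 |

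The holiday values alone contribute -2.0, -2.1 and -1.1. The gap between cohorts is -3.5, -2.3 and -1.1.

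**Sensitivity**
- *Baseline handling and build-up.* With one baseline value and gradual build-up at the 70-hour half-life, SILK gives -10.1, -4.9 and -2.2 with the holiday values and -6.6, -2.3 and -0.9 without. The holiday part is then -3.5, -2.6 and -1.3. The other cohort gives -7.2, -2.7 and -1.1. A pure on/off step with one baseline value goes slightly further at 6 months: -9.8 against -5.6.
- *Rise and baseline eGFR, 12 months, table model.* SILK against the other cohort is -3.2 against -1.8 (rise 7.5%, baseline 57.5; also rise 13%, baseline 35), -7.4 against -4.2 (13%, 80) and -8.3 against -4.7 (22%, 57.5).
- *End-of-Study sample included, full reversal.* SILK -3.5, -2.6 and -1.1; other cohort -0.2, -0.5 and -0.1. Both are shallower, and SILK stays steeper.

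**Check of the remedy.** On-drug values alone give 0 in the table model. With gradual build-up, dropping baseline and holiday values leaves -1.4, -0.6 and -0.3, and starting at Month 3 in SILK leaves about 0. An on/off-drug indicator in the table model leaves -0.2 to 0.

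**The case against.** **The other cohort is not clean either.** A reader might infer that SILK shows a spurious decline and the other 50 mg daily cohort shows none. The schedules do not support that. The off-drug baseline gives the other cohort -8.0, -3.0 and -1.2, and at 6 months -9.5 of SILK's -11.5 has nothing to do with the holiday. Only the additional part belongs to the holiday.

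**The SAP does not call these values on-treatment.** This is correct: it is silent on drug status. Inclusion follows from "the second using all of the available timepoints". One could answer that SAP 3.7 uses 6, 12, 18 and 24 months for eGFR, and that the holiday draws were meant only to test reversibility. But those times belong to the primary analysis, and nothing carries them into 3.7.2.1.

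**Might the other cohort have a holiday too?** Protocol 9.3.4 sits under a heading that also covers Phase 2a 50 mg daily. The synopsis, Table 4-2 footnote n and Sections 7.2.2 and 11.1 all limit the holiday to Phase 1b.

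**The size rests on an expectation.** Reversal is expected, not yet shown, and the 13% is a median from nine Phase 1b subjects. Partial reversal would shrink the effect in proportion, roughly. This stands.

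**The consequence is limited.** The analysis is post hoc, with no test or decision rule, and the primary analysis also reports a cystatin C equation at times that miss the holiday. This stands too and limits the weight of the point.

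**Conclusion.** The point holds in this form: applied as written, the all-timepoints slope adds a spurious decline to SILK beyond the artefact that both Phase 2a 50 mg daily cohorts share. At a 13% rise and baseline 57.5, the holiday samples add about 1 to 3.5 mL/min/1.73 m² per year, depending on follow-up and baseline handling, against an expected decline of about 5 per year. The effect shrinks with longer follow-up and scales with the rise and with baseline eGFR. It assumes full reversal off drug. SILK was steeper than the other cohort in every scenario run.

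It would be wrong to infer that removing the holiday samples repairs the slope: that leaves -9.5, -3.2 and -1.2. Nor is the first-and-last method a clean alternative. The holiday does not touch it, but with an on-drug last value it carries the whole step in both cohorts: -7.6 × 365.25/336 = -8.2 per year at 12 months (Day 336). If the 50 mg cohorts were pooled, the contrast would vanish but most subjects would still carry the artefact.

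This should be changed, but it does not affect the primary analysis.

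**What to change.** In SAP 3.7.2.1, compute the all-timepoints slope from on-drug values only. Exclude:
- Screening and Day 1 predose;
- every sample from the start of a protocol drug holiday through the predose restart sample, in SILK and in Phase 1b;
- the End-of-Study sample 30 days after the last dose;
- preferably also the early samples taken before the creatinine step has stabilised, including those just after the restart.

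Alternatively, keep all samples and add an on/off-drug indicator to each subject's regression, with baseline coded off drug.

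The cost is SAP wording and a filter on dosing dates. No new data are needed, and treatment and visits do not change. About six or seven eGFR values per SILK subject leave this one analysis (Screening, Day 1 predose, four holiday values, End-of-Study), and more if the early samples are dropped. Individual slopes become somewhat less precise, most of all for subjects with short follow-up.

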3.8 Safety Analysis

Safety assessments will include AEs, serious adverse events (SAEs), vital sign measurements, clinical laboratory evaluations (hematology and chemistry), and electrocardiograms (ECGs). Unscheduled visits for safety assessments will not be presented in summary tables but will be in listings. All safety analyses will be performed using the safety population for all cohorts and both studies.

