14.3.8 Safety Data

Safety analyses will be performed on all subjects who receive any quantity of study drug. AEs that are unrelated to treatment and that occur more than 30 days after the administration of the last dose of treatment will not be reported or analyzed. Safety evaluation will be performed based on the actual study treatment a subject has received. A separate set of safety analyses will be presented for the Phase 2a cohort.

Safety observations and measurements include AEs, safety laboratory tests, vital sign measurements, physical examinations, pregnancy status, echocardiograms, ECG assessments, and pharmacokinetic data.

Adverse events will be summarized both overall and by dose cohort and tabulated by severity and relationship to tesevatinib (causality). The original terms used by investigators to identify adverse events in the eCRFs will be mapped into preferred terms using MedDRA® (Version 18.1 or higher). Adverse events will then be grouped by MedDRA® preferred terms into frequency tables according to body system. The number and percentage of subjects experiencing adverse events will be tabulated by body system and preferred term both overall and by dose cohort. When an adverse event occurs more than once, the maximum severity and causality will be counted. Additionally, serious adverse events, adverse events that are related to tesevatinib, and adverse events that are unrelated to tesevatinib will be summarized separately. Concurrent illnesses will be listed and examined as possible confounders in the treatment relationship. Finally, any other potentially related adverse events will be analyzed and discussed, as necessary. Concurrent medications/therapies will also be listed.

A listing of all AEs and SAEs by subject will also be provided. The duration of AEs will be determined and included in listings, along with action taken and outcome. Incidence of laboratory abnormalities will be summarized. The worst on-study grade after the first dose of study drug will be summarized. The incidence of NCI-CTCAE Grade ≥ 3 (Version 4.03) laboratory abnormalities under treatment and shifts in toxicity grading from baseline to highest grade post-baseline will be displayed. Results for variables that are not part of the NCI CTCAE (Version 4.03) will be presented in the listings as below, within, and above the normal limits of the local laboratory. Pregnancy test results will be summarized by time point and dose cohort.

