Iothalamate testing will be evaluated as data are received to ensure that testing is consistent with no effect on renal function.

Vital sign measurements will be summarized at each scheduled time point using descriptive statistics. Physical examination results will be summarized by scheduled time point. Physical examination results will also be presented in the subject data listings. Physical findings including height and weight will be presented for each subject by visit and dose cohort.

Digital ECG results and wave intervals measurements will be summarized and reported by subject visit and dose cohort and/or as appropriate. QTc(F) prolongation results will be

summarized separately. Covariate analyses will be employed as necessary (eg, QTc[F] interval vs. plasma drug concentration).

Echocardiogram results will be summarized and reported by subject visit and dose cohort and/or as appropriate.

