3.8.1 Adverse Events

AEs will be coded using the MedDRA dictionary (Version 20.1 or higher). Treatment-emergent AEs (TEAEs) are any AE occurring or worsening in severity after the first administration of study medication. All AEs (including SAEs) will be graded using the 5-point Common Terminology Criteria for Adverse Events (CTCAE) V5.0 scale (mild, moderate, severe, life-threatening, or death). Causality with KD019 will be classified as: definitely related; probably related; possibly related; unlikely related; unrelated; or not related.

The number and percentage of patients who experienced at least one TEAE as well as the number and percentage of patients who experienced AEs of each specific SOC and PT will be presented. For the presentation of AE incidences, the SOCs and the PTs within each SOC will be presented by decreasing total frequency. Tabulation by maximum severity and relationship to tesevatinib will also be included by treatment group.

The TEAEs, Grade ≥ 3 TEAEs, SAEs, and TEAEs leading to dose modification/discontinuation will be summarized by treatment arm, SOC, and PT. These analyses will be repeated for events considered related (definitely related/probably related/possibly related) to tesevatinib.

Subject listings will be provided for SAEs, AEs resulting in study drug discontinuation and deaths.

Adverse events will also be presented in listings. Time to onset and duration of AEs will be included in listings, along with action taken and outcome.

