3.8.2 Clinical Laboratory Evaluation

The summary statistics (including number, mean, standard deviation, median, minimum and maximum) of all laboratory variables and changes from baseline will

be calculated for each visit or study assessment by treatment group. For parameters of white blood cell counts, neutrophils (absolute count), lymphocytes (absolute count), monocytes (absolute count), hemoglobin, platelets, ALP, ALT, aspartate aminotransaminase, total bilirubin, plots of mean/mean changes from baseline with the corresponding standard error will be displayed.

For shift tables, laboratory results will be classified using the CTCAE Version 5.0. All graded laboratory parameters will be summarized separately for hematology and biochemistry. Corresponding shift tables comparing baseline to the worst post-baseline grade within the treatment period will be provided.

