3.8.4 ECG

Descriptive statistics for ECG parameters (i.e., PR interval, QRS interval, and QTcF interval) at each time point with triplicate ECGs will be presented for the values and change from baseline scores. (QTcF is the QT interval using Fridericia's correction which is calculated by $QTcF = QT/RR^{1/3}$.)

The number and percentage of subjects with observed QTcF values that satisfy the following conditions will be presented by treatment group and study visit and categorized as: ≤ 450 ms; > 450 to 480 ms; > 480 to 500 ms; and > 500 ms.

The number and percentage of subjects having change from baseline QTcF values that satisfy the following conditions will be presented by treatment group and study visit and categorized as: ≤ 0 ms; > 0 to ≤ 30 ms; > 30 to ≤ 60 ms; and > 60 ms.

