	Table 14.4.15 Summary of Clinical Laboratory: Chemistry
	Table 14.4.16 Summary of Clinical Laboratory: Any Other Clinical Labs
	Table 14.4.17 Shifts from Baseline for Hematology Assessment
	Table 14.4.18 Shifts from Baseline for Chemistry Assessment
	Table 14.4.19 Summary of Vital Sign Results and Change from Baseline
	Table 14.4.20 Summary of 12-Lead ECG and Change from Baseline
	Table 14.4.21 Summary of QTcF Interval Results
	Table 14.4.22 Overall Summary of AEs
	Table 14.4.23 Overall Summary of AEs for Study 101
	[REDACTED]
Listings (16.2.Y.Z)	Listing 16.2.1 Disposition of Subjects
	Listing 16.2.2 Protocol Deviations
	Listing 16.2.3 Patients Excluded From Efficacy Analysis
	Listing 16.2.4 Patient Demographics
	Listing 16.2.5 Dose Changes
	Listing 16.2.6.1 Estimated Glomerular Filtration Rate

	Listing 16.2.6.2 Height Adjusted Total Kidney Volume
	Listing 16.2.7.1 Adverse Events
	Listing 16.2.7.2 Adverse Events leading to Study Drug Discontinuation
	Listing 16.2.7.3 Adverse Events leading to Death
	Listing 16.2.7.4 Serious Adverse Events
	Listing 16.2.8.1 Clinical Laboratory: Hematology
	Listing 16.2.8.2 Clinical Laboratory: Chemistry
	Listing 16.2.8.3 Clinical Laboratory: Any Other Clinical Labs
	Listing 16.2.8.4 Vital Signs
	Listing 16.2.8.5 12-Lead ECG
Efficacy	
Figures (14.3.Y.Z)	Figure 14.3.1 Annualized Change in Estimated Glomerular Filtration Rate
	Figure 14.3.2 Annualized Percent Change from Baseline Height Adjusted Total Kidney Volume

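### SAP 3.8 bars unscheduled visits from safety summary tables without exception, which leaves worst-grade laboratory tables ambiguous and off-schedule ECGs outside every QTcF category

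*SAP*

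**What the plan says.** The rule on unscheduled visits is one sentence in SAP 3.8: "Unscheduled visits for safety assessments will not be presented in summary tables but will be in listings". The SAP does not mention unscheduled visits anywhere else.

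Three later parts of the SAP have to be read with it:

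- **Adverse events, SAP 3.8.1.** "Treatment-emergent AEs (TEAEs) are any AE occurring or worsening in severity after the first administration of study medication". This definition does not depend on visits.
- **Laboratory, SAP 3.8.2.** By-visit statistics come first. Then, separately, "shift tables comparing baseline to the worst post-baseline grade within the treatment period will be provided". No limit to scheduled visits is stated.
- **ECG, SAP 3.8.4.** The counts of subjects by QTcF value, and by change from baseline, "will be presented by treatment group and study visit and categorized as" the listed ranges. There is no row for the highest value at any time. The only QTcF-specific output in SAP section 4 is "Table 14.4.21 Summary of QTcF Interval Results".

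Protocol 14.3.8 says of laboratory data: "The worst on-study grade after the first dose of study drug will be summarized". It adds that "shifts in toxicity grading from baseline to highest grade post-baseline will be displayed". For ECGs it says: "Digital ECG results and wave intervals measurements will be summarized and reported by subject visit and dose cohort and/or as appropriate". It also promises a separate summary of QTc(F) prolongation, without saying what form that takes.

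**The concern.** A by-visit table and a worst-case table answer different questions. Leaving unscheduled values out of a by-visit table keeps each column comparable. Leaving them out of a worst-case table can remove the value the table is meant to find, because off-schedule tests are often done when something is suspected.

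The protocol generates such tests. Section 9.8 allows ECGs and laboratory tests at unscheduled visits. Section 11.3.1 calls for electrolytes and an ECG when significant diarrhea develops. Section 11.3.3 calls for an ECG when there are symptoms of arrhythmia. Section 13.3.8 has clinically significant laboratory abnormalities repeated promptly. Beyond 12 months, scheduled visits are two months apart (section 9.6), so an event between visits is more likely to be documented only off schedule.

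Two things are at stake. Two programmers could follow the SAP faithfully and produce different laboratory shift tables. And the QTcF outlier tables may omit the tracings taken because of a suspected problem, in a trial where QTc prolongation was a stated reason for not taking 100 mg daily forward (protocol 5.4.2).

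**Working it through.** The plan gives no figure to reproduce. The check sets the texts side by side and then works out the direction and the unit size of any effect.

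**1. Does the rule reach adverse events?** No sensible reading allows that. SAP 3.8.1 counts any event after first dose, however it came to light. The question is confined to measured safety data.

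**2. Laboratory worst grade.** Let A be all post-baseline results in the treatment period, and S the subset from scheduled visits.

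- SAP 3.8.2 on its own: worst grade = max over A.
- SAP 3.8 applied literally: worst grade = max over S.
- Protocol 14.3.8: worst and highest grade, with no limit to S.

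Both SAP readings are available, so this is an ambiguity and not a proven exclusion.

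**3. Which period?** The SAP does not define the treatment period. Protocol 7.2.2 uses the term for the initial 28 days when describing Phase 1b, but the section carrying that heading continues to treatment for 24 months. The set A is therefore also undefined at its end.

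**4. QTcF categories.** Each cell in SAP 3.8.4 is indexed by treatment group and study visit. An ECG from an unscheduled visit has no visit index, and there is no any-time row to catch it. If an event-triggered ECG happens to fall on a scheduled visit, it can still be counted. Otherwise it appears only in Listing 16.2.8.5.

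**5. Direction.** S is contained in A, so max over S ≤ max over A for every subject. With baseline held fixed, the number of subjects above any threshold under the literal rule is equal to or lower than the number using all results. It cannot be higher.

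**6. Unit size.** The documents do not give the number of unscheduled tests, and only subjects whose sole outlying value is off schedule are affected. With the group size as a fixed denominator, each such subject changes the incidence by 1/n:

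| Group (source) | n | 1/n |
|---|---|---|
| 50 mg QD group (protocol 14.2) | 65 | 1.5 points |
| SILK, if full (protocol 7.2) | 50 | 2.0 points |
| Cohort 1 (protocol 5.2.2.2.3) | 9 | 11.1 points |
| Cohort 2 (same) | 8 | 12.5 points |
| Cohort 3 (same) | 5 | 20 points |

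These show what one subject weighs. They do not estimate how many there are.

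**7. What the adverse event route catches.** Protocol 9.10 says that a centrally read QTcF of at least 480 msec, or more than 60 msec above baseline, calls for further monitoring. The same section makes an ECG abnormality that changes management, including by added monitoring, an AE record. Protocol 13.3.8 sends all severe and life-threatening laboratory abnormalities to the AE form. The extremes should therefore reach the AE tables, although those tables do not fill the numeric QTcF categories.

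**8. Which tracings count as on treatment?** If a maximum is added, some scheduled ECGs are effectively off drug. Using the half-life of about 70 hours in protocol 5.4.2 and assuming first-order decline:

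- SILK Month 2 predose ECG, about 28 days off drug: 672/70 = 9.6 half-lives, residual about 0.13%.
- End-of-Study ECG at 30 days: 720/70 = 10.3 half-lives, residual about 0.08%.

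At 92 hours, the top of the range in protocol 5.2.2.3, the residuals are still only 0.63% and 0.44%. Such tracings need a flag.

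**The case against.** The strongest reply has four parts.

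**The laboratory point is only wording.** A specific rule on worst grade would normally prevail over a general one on visits, and many programmers would read it that way. That is fair, and it is why the point is an ambiguity. One clarifying sentence settles it.

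**The ECG analysis may sit elsewhere.** The protocol synopsis promises a prospective plan for the ECG data, and protocol 5.3.1 reports time-averaged, time-point and concentration analyses of QTc that this SAP does not contain. A maximum-value summary may exist in a document not available here. That stands as a limit. However, SAP 3.8.4 does not refer to such a plan.

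**The events are captured anyway.** Arrhythmia symptoms and significant diarrhea would themselves be reported as AEs, and confirmed QTcF extremes should be. This holds for the extremes and limits the harm.

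**The remedy is incomplete.** Protocol 9.8 does not say that unscheduled laboratory tests go to the central laboratory, and protocol 9.9 bases the final analysis on central results. Locally run tests would stay in listings. This also stands.

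A reader might go further in three ways that the documents do not support:

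- *The SAP contradicts the protocol on QTcF.* Protocol 14.3.8 asks for ECG results by visit or as appropriate and does not require a maximum. The QTcF part is a gap.
- *The modelled mean rise of 13.3 ms at 50 mg puts subjects in the > 450 to 480 ms range unseen.* That figure is a prediction at mean Cmax. Protocol 5.3.1 places the observed peak at 4 hours on Day 14, when SILK has a scheduled ECG (protocol 9.10), so it says little about what is seen only off schedule.
- *The rule can never raise a count.* If it also removed an unscheduled pre-dose repeat, the baseline in SAP 3.1.5 could change, and change or shift categories could move either way.

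**Conclusion.** The point holds as one ambiguity and one gap. The sentence in SAP 3.8 has no stated scope. Applied literally, it narrows the laboratory worst-grade and shift tables to scheduled visits, and the by-visit layout of SAP 3.8.4 gives an off-schedule ECG no QTcF category.

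Provided that only post-baseline values are dropped and baseline is unchanged, worst-case counts can be understated but not overstated. The amount cannot be derived from the documents. No data are lost, since everything is listed, and the most serious values have a second route through AE reporting. The weight is minor to moderate. The change is worth making because the possible error runs in the unfavorable direction for safety and the correction is cheap.

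The QTcF part assumes that no separate ECG plan already supplies a maximum-value summary.

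**What to change.** 1. **SAP 3.8.** State that unscheduled values are excluded from by-visit summaries only.
2. **SAP 3.8.2.** Base the worst-grade and shift tables on all post-baseline central-laboratory results in the treatment period, scheduled and unscheduled, and define that period with a start and an end. Results available only from a local laboratory stay in listings, in line with protocol 9.9.
3. **SAP 3.8.4, or the separate ECG plan if there is one.** Add the existing value and change categories for each subject's maximum post-baseline QTcF and maximum change from baseline, over all centrally read ECGs, scheduled and unscheduled. Use the triplicate mean where there is one and say how single tracings are handled. Flag tracings taken off drug: the drug holiday including the Month 2 predose ECG, drug holds, and End of Study.

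The cost is a few sentences and a little programming. The values are already collected and listed, and protocol 9.10 has all ECGs analyzed centrally. The downside for the sponsor is that outlier rates may look slightly worse.
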